Patients may withdraw from the trial at any time at their own request or they may be withdrawn at any time at the discretion of the investigator if it is considered to be in the best interest of the patient. Patients can withdraw without giving a reason, but if a reason is given this should be documented in the eCRF and medical notes. It is possible for a patient to withdraw from treatment but continue to be followed up via eCRF, in clinic or by telephone. A 'Withdrawal from Treatment' eCRF will be completed. If patients do not wish to continue in this way, an 'End of Study' eCRF will be completed and they will not have any further visits.

The main analyses will be by intention to treat, therefore, data and samples collected up to the time of withdrawal of consent will be included in the study analyses, as stated in the consent form. Such data or samples will be included in the analysis, unless explicitly forbidden, again, in writing by the participant.

Patients may be withdrawn from trial medication, and/or the study in the event of:

- Unacceptable toxicity/intolerable side effects
- Inter-current illness
- Patient withdrawing consent
- Patient unable to comply with the study schedule
- Interruption of study drug intake for greater than 60 days
- Patient chooses to come off Active Surveillance and undergo active therapy
- Rise in serum calcium above upper limit of normal or 2.65mmol/l
- Identification of higher risk disease unsuitable for surveillance following 'For Cause' repeat prostate biopsy precipitated by an increasing PSA
- Development of new dyspeptic symptoms, or any sign of gastro-intestinal bleeding (haematemesis, melaena, decreased haemoglobin)
- Any episode of haemorrhage or development of a bleeding disorder
- Development of a condition not compatible with the study, or the addition of a new incompatible medication e.g. NSAID, or other product as in section 4.10
- Disease progression

Data concerning toxicity will be collected using the diary cards issued to all participants, which will allow symptoms to be classified as mild, moderate or severe. Data will also be collected on the Case Report Forms regarding gastro-intestinal bleeding and hypercalcaemia. Blood calcium levels will be monitored six monthly and any emergency hospital admissions reported, in which hypercalcaemia is identified, will be documented and followed up by the research team.

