Patients who interrupt study drug intake for a cumulative total of greater than 60 days, in a 3 month period between follow-up appointments, will be considered as non-compliant and will be discontinued from the study. An 'End of Study, eCRF will be completed, and no further follow-up appointments conducted. These patients will be included in the intention to treat and safety analyses. They will be included in the efficacy assessment only if they have received at least three 90 day cycles of treatment.

Patients will be considered to be lost to follow-up if there has been as no contact for ≥6 months from the last scheduled clinic visit. These patients will be included in the intention to treat and safety analyses. They will be included in the efficacy assessment only if they have received at least three 90 day cycles of treatment.

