Administration of IMP will be discontinued in the following circumstances:

- Development of hypercalcaemia confirmed by blood sample
- Development of new dyspepsia symptoms or gastro-intestinal bleeding
- Development of a condition which requires treatment with a prohibited concomitant therapy
- Development of a condition which, in the judgement of the investigator, adversely affects the participant's safety, compliance or ability to complete evaluations
- If the investigator concludes that this course of action is in the participant's best interests

Should a patient become concerned that a symptom is potentially related to a study medication, it would be preferable to consider a dose interruption e.g. an alternate daily dose, or offer a 'treatment holiday', rather than stop treatment completely. Dose interruptions can be up to 30 days in the case of suspected toxicity. Longer 'treatment holidays' must be discussed with the PROVENT CCO. However, patients who interrupt study drug intake for a cumulative total of greater than 60 days, in a 3 month period between follow-up appointments, will be considered as non-compliant and will be discontinued from the study. An 'End of Study, eCRF will be completed

'Treatment holidays' can also be used in other special circumstances, at the discretion of the PI, but any dose interruptions of greater than two weeks, for reasons other than toxicity must be discussed with the PROVENT CCO. All variations in dose regime/daily dose, must be documented on the relevant eCRF, & in the patient diary.

Full treatment may be restarted after an appropriate interval, (no longer than 60 days), if symptoms have resolved, or a decision may then be made about withdrawal, if symptoms persist. Any variation in dose regime should always be documented on the relevant Case Report Form and in the patient diary.

Participants who discontinue the study drugs for any reason will not be considered to have left the study, and will be followed up for primary and secondary outcome measures. These patients will be included in the intention to treat and safety analyses.

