5.12 Data Collection and Follow Up for Withdrawn Subjects

Data collected up to the time of withdrawal of consent will be included in the study analyses, as stated in the consent form, unless participants specifically withdraw permission to do so in writing. With the exception of such patients, withdrawn subjects will remain under three monthly follow-up in clinic for the duration of the trial, as the main analyses will be by intention to treat.

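### The 60-day interruption rule in sections 3.4 and 4.11 takes men out of the study, and 3.4 ends their visits, while the close of 4.11 and section 5.12 keep men who stop drug in follow-up

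*Protocol*

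**What the plan says.** Two sets of instructions cover a man who stops taking his allocated drug.

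**Leave the study.** Section 3.4 sets a trigger: a cumulative interruption of more than 60 days within a three-month period between follow-up appointments. Such a man is treated as non-compliant and discontinued from the study. An End of Study "eCRF will be completed, and no further follow-up appointments conducted". He nevertheless stays in the intention-to-treat and safety analyses. For a separate efficacy assessment, 3.4 adds: "They will be included in the efficacy assessment only if they have received at least three 90 day cycles of treatment". Section 4.11 repeats the trigger, says that such patients "will be considered as non-compliant and will be discontinued from the study", and again calls for the End of Study form. It does not itself say that visits stop.

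**Stay in follow-up.** The last paragraph of the same section 4.11 says: "Participants who discontinue the study drugs for any reason will not be considered to have left the study, and will be followed up", and it refers to both primary and secondary outcomes. Section 5.12 says that "withdrawn subjects will remain under three monthly follow-up in clinic for the duration of the trial", and gives as its reason that the main analyses are by intention to treat. Its only stated exception is a man who withdraws permission in writing.

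**The concern.** These are instructions to sites about which data to collect, and they point in opposite directions for the same man. Section 3.4 also counts him in the intention-to-treat analysis while ending the visits that would supply his outcomes.

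At stake are the secondary progression outcomes. Section 8.2 defines biochemical progression by PSA at 12 months, and the repeat MRI and biopsy are also 12-month assessments. The mixed model on log(1+PSA) in section 8.5 uses the PSA series. Section 1.5 says that the disease progression rate will inform the numbers needed for the definitive trial, so these outcomes matter even in a feasibility study. Section 4.11 allows interruption for suspected toxicity, so losses could differ between arms.

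**Working it through.** **1. Figures in the plan.** No stated figure depends on this rule. The only power figure is the 89% in section 8.4, for recruitment: 300 men approached, 33.3% against 25%, two-sided 0.05. By normal approximation:

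- z = [0.333 − 0.25 − 1.96 × √(0.25 × 0.75/300)] / √(0.333 × 0.667/300) = (0.083 − 0.049)/0.0272 = 1.25
- power = 89.4%

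The figure reproduces, and no follow-up rule changes it.

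**2. Can both instructions be obeyed?** Take a man who stops both products for good 30 days after randomisation. At the month 3 visit (about day 91) he has been off drug for 91 − 30 = 61 days, which is more than 60.

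| Text | Status | Further visits |
|---|---|---|
| 3.4, 60-day rule | discontinued from the study | none |
| 4.11, 60-day sentence | discontinued from the study, End of Study form | not stated |
| 4.11, last paragraph | has not left the study | followed for outcomes |
| 5.12 | withdrawn subject | three-monthly to the end of the trial |

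The first row cannot be reconciled with the last two. A man who stops later in an interval normally meets the trigger in the next one.

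**3. What is lost if 3.4 is followed.** Appendix 1 lists post-baseline PSA at months 3, 6, 9, 12, 15 and 18, which is 6 visits (section 5.7 also describes PSA as three-monthly). A man closed at month m loses 6 − m/3 of them.

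| Closed at month | PSA visits lost | Month-12 outcomes |
|---|---|---|
| 3 | 6 − 1 = 5 | PSA, MRI and biopsy lost |
| 6 | 6 − 2 = 4 | PSA, MRI and biopsy lost |
| 9 | 6 − 3 = 3 | PSA, MRI and biopsy lost |
| 12 | 6 − 4 = 2 | usually in hand, but biopsy may be pending |
| 15 | 6 − 5 = 1 | usually in hand |

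The month-12 entry follows from section 5.4, which allows the repeat biopsy from week 48 to week 56, so up to four weeks after the nominal visit.

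**4. Size per man.** One man is 1/102 = 0.98 percentage points of a cohort proportion and 1/17 = 5.9 points of a single arm.

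**5. Number of men.** The protocol gives no rate of long interruption. Purely as an assumption, if 5% to 20% of the 102 men were closed before month 12, that would be about 5 (102 × 0.05 = 5.1) to 20 (102 × 0.20 = 20.4) men. With nothing assumed about their outcomes, the cohort progression proportion would be uncertain by the same 5 to 20 points.

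**The case against.** **Interrupting is not the same as discontinuing.** One could try to reconcile the texts this way. It does not work: the last paragraph of 4.11 applies whatever the reason for stopping, and 5.12 covers withdrawn subjects with a single exception.

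**The consequence is modest.** This stands in large part. The primary endpoint is recruitment. A shortened PSA series does not remove a man from a mixed model. Data up to withdrawal are kept, and the pre-18-month withdrawal column in section 5.5 and Appendix 1 captures values at exit. That column cannot supply month-12 outcomes for a man who left at month 3, 6 or 9, however, and takes MRI and biopsy only if done. Handling of missing data may be left to an analysis plan, but no analysis plan recovers results that were never recorded.

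**Stronger readings that the text does not support.**

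- *That none of these men could reach three 90-day cycles, so all are already outside the efficacy assessment.* Three cycles are 3 × 90 = 270 days. A man off both products for at least 61 days has at most 274 − 61 = 213 days of drug by month 9. But tablets and oil are separate products, and 3.4 does not say whether interrupting one is enough. A man who stopped only the tablets could have about 274 days of oil by month 9. He could also qualify if received means elapsed or dispensed cycles.
- *That section 3.4 contradicts itself.* Its earlier list says "Patients may be withdrawn from trial medication, and/or the study in the event of" and includes "Interruption of study drug intake for greater than 60 days". That entry has no three-month window, and a permissive list followed by a specific rule is ordinary drafting. The same section's statement that an End of Study "eCRF will be completed and they will not have any further visits" concerns men who choose not to continue follow-up.
- *That men with dyspepsia, gastrointestinal bleeding or intolerance also lose follow-up.* Sections 4.5 and 4.11 describe them as withdrawn from the study, but neither ends their visits, and 5.12 covers withdrawn subjects. This is loose labelling only.

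**Conclusion.** The conflict is real and no reading removes it. The 60-day rule in 3.4, with the matching sentence in 4.11, contradicts the last paragraph of 4.11 and section 5.12. If sites follow 3.4, men closed at month 3, 6 or 9 lose all three month-12 progression assessments and 5, 4 or 3 of 6 PSA visits, and a man closed at month 12 may lose a pending biopsy. These men still count in the intention-to-treat analysis.

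The size in this trial cannot be stated: the number of men is unknown, and imbalance between arms is a possibility, not a finding. A reader might infer that the feasibility conclusion is at risk. It is not, because recruitment does not depend on follow-up after randomisation. The point is worth correcting because the loss is avoidable and cannot be undone later.

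**What to change.** In the 60-day rule of 3.4 and the matching sentence of 4.11, replace discontinuation from the study, the End of Study form and (in 3.4) the end of appointments with:

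- discontinuation of study medication;
- the Withdrawal from Treatment form that 3.4 already provides;
- continued recording of routine three-monthly PSA and the 12-month MRI and biopsy, unless the man withdraws consent or has radical therapy.

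As a minor tidy-up, change withdrawal from the study to withdrawal from study medication in 4.5 (intolerance) and 4.11 (dyspepsia or bleeding). The safety rules for stopping drug stay as they are.

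The cost is a wording amendment and a little extra form entry for men off drug. Section 5.4 already describes the three-monthly appointments and the 12-month MRI and biopsy as routine care, so no new procedures are needed.

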4.12 Return/Recall or Destruction of IMP

At the termination of the study, or at the request of the sponsor, any unused study drug remaining must be destroyed according to local standard procedures, and should be documented and accounted for in the pharmacy Accountability/Destruction Logs. A copy of the Drug Destruction Form should be filed in the PROVENT pharmacy file.

Unused products that have passed their expiry date or have insufficient shelf life must be entered onto the Drug Accountability/Destruction Log. A copy of all destruction logs must be signed by pharmacy staff and returned to the sponsor to confirm destruction.

Participants will be asked to return unused medication to the research clinic staff who will then return the pack to pharmacy. The pharmacist will document the quantities on the Dispensing Log, and these details will be collected by a member of the research team at regular intervals for recording on the CRF. The pharmacy will record the pack numbers and quantity of tablets/oil on the Accountability/Destruction Log, and the IMPs may then be destroyed according to local practice.

5.0 Study procedures

All procedures are summarised in the Schedule of Assessments table in section 5.5

5.1 Informed Consent Procedures

Potentially eligible patients who have been recently diagnosed with prostate cancer will be identified by the clinical team in the outpatient clinic, having undergone MRI scanning and systematic and/or targeted prostate biopsy. In addition, patients already managed by Active Surveillance may be eligible for PROVENT providing they have undergone disease reclassification (prostate biopsy plus MRI imaging) within the previous 12 months. These patients will be identified in the follow up clinic by the clinical staff.

The clinical care team at each site will be responsible for informing the patient of his diagnosis and discussing the available treatment options, including (if appropriate) Active Surveillance. Patients for whom Active Surveillance is a treatment option will be assessed by a clinician for study eligibility and, if suitable, will be given a Patient Information Sheet (PIS) explaining the PROVENT study. This will be documented in the patient's notes.

The Investigator will discuss the study with the patient, and, if interested, the Investigator or a trained member of the research team will explain the study in more detail. The patient's details will be added to the locally held Pre-screening Log, using only his initials and day (dd, 1 to 31) of birth as identifiers. The patient will then be given a further appointment to return and discuss their preferred treatment with the Investigator as per normal practice, giving at least 24 hours to consider his treatment options and read the PIS.

The Principal Investigator is responsible for ensuring that participants are fully aware and understand all the requirements expected of them. If the Investigator has concerns about a patient's understanding of the trial and PIS, and/or of their ability to adhere to the protocol requirements, the patient will not be entered into the trial.

At the follow up appointment, the clinician/Investigator will discuss the patient's choice of treatment, and, if his preferred option is Active Surveillance, his interest in the trial will be established. Should he wish to take part in the research written informed consent will be obtained before proceeding further and he will receive a pre-randomisation ID,

The Investigator, or a Research Nurse trained in taking informed consent (as documented in the Site Delegation Log), is responsible for obtaining written informed consent from each subject prior to participation in any study specific procedures. This follows a full explanation of the aims, methods, anticipated benefits and potential hazards of the study. Participants will be reassured that they are free to refuse all involvement in the study, or may withdraw their consent at any time, and for any reason with no effect on their standard of care.

The informed consent consultation should take place in a confidential appropriate environment. Neither the PI, nor any other trial staff should coerce or unduly influence a patient's decision to participate or continue to participate in the trial. All questions about the study should be answered to the satisfaction of the patient. This should occur prior to consent being obtained and the consent form signed.

For the consent to be valid, each box on the consent form should be initialled, and the consent form must be signed and dated by both the person taking consent and the person giving consent at the same occasion. Each person should clearly print their name by their signature and date only their own signature. Where consent is taken by someone other than the Investigator, the Investigator must be readily available to ensure medical oversight, and must countersign the consent form prior to the patient receiving their first dose of IMP.

Once all parties have signed and dated the consent form, the original must be filed in the Investigator file. In addition, a copy of the form must be given to the participant, and a further copy must be filed in the patient's notes. A record of the discussion should be made by the Investigator in the medical notes.

Both the PIS and CF should be printed on local trust headed paper for the trial site where the patient is consented, and should show the date and version number. The contact details of the person/s to contact for further information about the study must also be given.

Should new safety information become available which may result in significant changes in the risk/benefit analysis, the PIS and Consent Form will be reviewed and updated accordingly. All participants actively involved in the trial will be informed of the updated information and given a copy of the revised

PIS and the correspondingly revised consent form to sign, in order to confirm their wish to continue in the study.

5.2 Screening Procedures

Recruitment will take place primarily in specialist prostate clinics at participating centres, and the locally held Pre-screening Log will be completed for each potentially eligible patient who will be given a copy of the Patient Information Sheet. The log will be completed with only the patient's initials and day (dd) of birth. If a patient is found to be ineligible, or does not wish to participate, the date of the visit and reason for non-participation will be added to the Pre-screening Log and the personal identifiers will be removed. The site is responsible for forwarding completed copies of their pre-screening logs, without personal identifiers, to the CCO at regular intervals.

Sites will be provided with a template study invitation letter, and poster advertising the trial, to assist with the recruitment process. In addition there is a trial website. The site address, www.provent.org.uk is provided to participants in the Patient Information Sheet and on the diary & wallet cards they will receive.

Once a patient has agreed to participate, and written informed consent has been obtained, the Investigator or a suitably trained member of the research team will be responsible for further screening of each subject prior to participation in the study. The pre-randomisation Eligibility Assessment CRF will establish whether the potential participant fulfils the eligibility criteria for the study.

Participants are required to have a corrected serum calcium level of 2.65mmol/l or less confirmed prior to commencing study medication. An existing serum result will be acceptable if taken within 2 months prior to the Eligibility Assessment date; alternatively, a further sample will be taken for this once consent has been obtained.

As an additional precaution, eligible patients will also be screened for *Helicobacter pylori*. This test will require the patient to bring a stool specimen to their randomisation appointment. A collection pot will be provided for this at the screening visit, and instructions given on how to collect the sample. The test should not be carried out within 4 weeks of antibiotic or 2 weeks of PPI use, as these may lead to false negative results. Patients will be given an alternative treatment if currently taking PPIs.

Patients whose H Pylori test is positive will be informed of the result and will require treatment for 7 days with an appropriate antibiotic and PPI therapy if they wish to continue in the study (see section 5.4).

Once all parties have signed the consent form, & screening has confirmed the patient's eligibility, the patient may be randomised and the outcome added to the locally held Pre-screening Log. At this stage the participant's status on the application will be updated from 'registered', to 'randomised'.

5.3 Randomisation Procedures

The principal method of randomisation will be by means of a bespoke web-based application, developed by Barts CTU, which will be accessible to all relevant research staff. Staff will be trained in the use of this application. The application eCRF will reaffirm patient eligibility and require confirmation that the consent form has been satisfactorily signed and countersigned.

Eligible participants will be randomised in a 6-arm 1:1:1:1:1:1 design to receive one of the following:

- 1. Aspirin 300mg + Vitamin D3
- 2. Aspirin 300mg + Vitamin D3 placebo
- 3. Aspirin 100mg + Vitamin D3
- 4. Aspirin 100mg + Vitamin D3 placebo
- 5. Aspirin placebo + Vitamin D3

6. Aspirin placebo + Vitamin D3 placebo

Randomised blocks will be used to maintain balance amongst these 6 arms. In addition, the aspirin placebo groups will be block randomised to either small or large aspirin placebo tablets.

The allocated unique study number will correspond to a particular arm of the trial. When a patient is randomised, a pack number associated with that patient's study number will be automatically generated by the PROVENT app. The pre-labelled packs containing the medication for that study number will already be in the pharmacy at that centre, labelled with a unique pack identification number.

In the event that the web application is unavailable, randomisations will be able to be made by an email or a FAX backup system.

Once the patient has been successfully randomised, this will be documented within the PROVENT application, and on the locally held PROVENT Pre-screening Log.

